sonography within 21 days of study start reveals no evidence of follicular development in the face of a negative pregnancy test.

Visits 1 through 5 will occur during the first week of the study protocol. During Visits 1 through 4, subjects will undergo an HCG stimulation test (HCG-ST) in the CRC consisting of a single IM HCG injection during Visit 1 after documenting a negative urine pregnancy test, along with a single blood draw during all 4 visits at 0, 24, 48 and 96 hours after HCG administration to measure serum androgens and 17-hydroxyprogesterone. Visits 1 through 3 will be short lasting ~30 minutes. After one of these short visits, subjects will also undergo a body composition assessment consisting of a whole-body dual-emission X-ray absorptiometry (DEXA) scan in the Integrative Physiology Laboratory (IPL) at [name], and a magnetic resonance image of the abdomen in the Center for Magnetic Resonance Research at [name]. Visit 4 will last ~8 hours during which a cream challenge test (CCT) will also be performed in the CRC consisting of dairy cream ingestion and serial blood draws at 0, 2, 3 and 5 hours after cream ingestion to measure inflammation markers. Visit 5 will last ~7 hours and occur 2 days after the CCT during which subjects will undergo a FS-IVGTT in the CRC to assess insulin sensitivity and glucose-stimulated inflammation.

[figure not shown]
| Table 1. PRE-STUDY SCREENING | | | | |
|--|---------|---|---|---|
| STUDY PROTOCOL | WEEKS → | 0 | 4 | 8 |
| Salicylate Level | | X | X | X |
| Sex Hormone Binding Globulin | | X | | X |
| Body Composition: MRI & DEXA | | X | | |
| HCG Stimulation Test: T, A & 17OHP @ 0, 24, 48 & 96 hours. | | X | | X |
| Cream Challenge Test: MNC-derived ROS, NFκB, RNA & protein inflammat'n markers @ 0, 2, 3 & 5 hours. | | X | | X |
| Frequently Sampled Intravenous Glucose Tolerance Test: glucose, insulin, C-peptide & FFA q 1-30 minutes x 34 samples from -20-240 minutes. | | X | | X |
| Post-Study Safety Tests: CBC & CMP. | | | | X |
| Ovulation Monitoring: BBT from 0-12 weeks; P on 7th day of BBT rise; If P >2 ng/dl documented, vaginal sonography on day of & day after LH surge. | | | | |

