- **Insulin-Modified FS-IVGTT:** The test will be performed in the CRC two (2) days after the CCT after an overnight fast of ~12 hours as described by Polidori et al.³² An intravenous polyethylene catheter will be inserted in an forearm vein at ~7:10 AM (-50 minutes) for infusing glucose and insulin. Another intravenous catheter will be inserted in a contralateral forearm vein for blood sampling. The size of the catheter (i.e. 18-23-gauge) will be of suitable caliber for the size of the vein used to gain access (*please refer to the Risks - Venipuncture / Venous Catheter Blood Sampling subsection of Section 7.0 for the approach and alternatives to intravenous catheter placement*). Baseline blood samples will be obtained at ~7:40 AM (-20 minutes), ~7:50 AM (-10 minutes), ~7:59 AM (-1 minute) and ~8 AM (0 minutes). The average of the four samples is considered the basal level. A glucose solution (0.3 gm/kg) will be administered intravenously beginning immediately after the 0 minute blood draw. Insulin (20 mU/kg Humulin; Eli Lilly, Indianapolis, IN) delivered in 1 unit/ml infused over 60 seconds starting at ~8:20 AM (20 minutes). Blood samples will be obtained at -20, -10, -1, 0, 1, 2, 3, 4, 5, 6, 7, 8, 10, 12, 14, 16, 19, 22, 23, 24, 25, 27, 30, 40, 50, 60, 70, 80, 90, 100, 120, 150, 180 and 240 minutes. Every attempt will be made to insert the intravenous catheters and obtain blood samples on time. However, all samples with the exception of those used to measure glucose may be obtained within a fifteen minute window after the scheduled time due to any unforeseen technical difficulty. A total of 272 ml of blood (8 ml/sample) will be collected during the entire procedure. All infusions will be stopped at 12 PM. Upon completion of the test, both catheters will be removed, and subjects will be fed a standard lunch. Plasma will be isolated from the blood samples collected and stored at -80° C until assayed for glucose, insulin, C-peptide and FFA. Preparation of glucose and insulin for infusion during the FS-IVGTT procedure will be performed by the UI Hospital Pharmacy Investigational Drug Services.

- *Mathematical Model to Assess Hepatic and Extrahepatic Insulin Clearance.* Hepatic and peripheral insulin clearances were estimated using a model for insulin kinetics during the FS-IVGTT as described in Fig. 3.

The model is based on the following main assumptions:

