6.2 Specimen Collection and Storage

- **Blood specimens** will be collected by venipuncture or from a venous catheter placed by a trained medical person who will remain at the bedside to monitor the subject continuously.
- For screening, a maximum of 22 mL (4½ tsp) will be drawn to measure hormones if not performed previously, a complete blood count and a chemistry panel, and 24 mL (5 tsp) will be drawn during the screening OGTT. During the study, we will draw 64 mL (12¾ tsp) during each HCG-ST (Visits 1-4 and 8-11), 330 mL (66 tsp) during each CCT (Visits 4 and 11), and 272 mL (54 tsp) during each FS-IVGTT (Visits 5 and 12). We will also draw an additional 20 mL (4 tsp) to measure salicylate levels (Visits 1, 6, 7 and 8) and fasting lipid profiles, and an additional 5 mL (1 tsp) to measure progesterone for ovulation detection as needed only if warranted by the BBT response.
- **MNC Isolation and Processing:** Blood samples are collected in tubes containing Na-EDTA as an anticoagulant. A 12 ml sample will be layered over 12 ml of polymorphonuclear cell isolation medium (Polymorphprep™, Accurate Chemical and Scientific Corporation, Westbury, NY). Samples will be centrifuged at 450 x g for 30 minutes at 18°C resulting in separation of two bands above the red blood cell pellet. MNC present in the top band will be harvested with a Pasteur pipette and washed repeatedly with Hank's buffered saline solution (HBSS) yielding greater than 95% pure MNC.⁴⁶ A fresh portion of MNC will be reconstituted

in HBSS for ROS generation or suspended in RPMI 1640 medium for culture. A second MNC portion will be suspended in RNAlater reagent (Qiagen, Germantown, MD) for 24 hours at 4°C to stabilize RNA, centrifuged at 6,000 x g for 5 minutes at 4°C to yield a pellet that will be stored at -80°C until processing for real time-PCR (RT-PCR). A third MNC portion will be suspended in phosphate buffered saline (PBS – pH 7.4), centrifuged at 13,000 x g for 2 minutes at 18°C to yield a pellet that will be stored at -80°C until processing for Western blotting. A fourth portion of MNC will be used to prepare nuclear extracts of DNA-binding protein with a method described by Andrews et al., and will subsequently be stored at -80°C until processing for electrophoretic mobility shift assays.⁴⁷

- Plasma and/or serum will be separated from whole blood through centrifugation and aliquoted into 1.5 ml polypropylene microtubes for storage.

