7.0 Expected Risks/Benefits

Risks

- **Venipuncture / Venous Catheter Blood Sampling** – For screening, we will draw a maximum of 22 mL (4½ tsp) to measure hormones if not performed previously, a complete blood count and a chemistry panel, and 24 mL (5 tsp) during the screening OGTT. During the study, we will draw 64 mL (12¾ tsp) during each HCG-ST, 330 mL (66 tsp) during each CCT, and 272 mL (54 tsp) during each FS-IVGTT. We will also draw an additional 20 mL (4 tsp) to measure salicylate levels and fasting lipid profiles, and an additional 5 mL (1 tsp) to measure progesterone for ovulation detection only if warranted by the BBT response.

The *Study Visit Blood Sampling Plan* included as an Appendix provides a detailed accounting of the volume of blood that will be drawn from each subject during the entire study. These flow sheets provide a detailed breakdown of the tubes that will be used, the volumes that will be drawn, and the types of measurements that will be performed. The *Laboratory Flow Charts* also included as an Appendix illustrates how the collected blood will be utilized for molecular work and cell culture in the PI's laboratory to effectively generate key data to address Aims of the study.

The total amount of blood that will be drawn on each subject during screening and the HCG-ST, CCT and the FS-IVGTT is expected to be <1,500 ml consisting of no more than 750 ml obtained ~12 weeks apart which again is a longer interval than the typical clinical practice standard for blood donations. All subjects will be screened for blood count. The decision to proceed with study participation will be reviewed on a case-by-case basis after taking into consideration the health status of the individual if the pre-study screen reveals a hemoglobin <11.6 grams; or in the case of a subject who weighs <70.8 kg, if the pre-study hemoglobin is <12.6 grams. In the latter case, blood sampling will be limited to 10.5 ml/kg within an 8 week period. If the complete blood count (CBC) performed during initial screening reveals evidence that low hemoglobin is due to iron deficiency anemia in an otherwise eligible volunteer, iron supplementation (ferrous sulphate 325 mg twice daily) will be recommended and a CBC will be performed at appropriate intervals until higher acceptable hemoglobin meeting the above criteria is documented before the volunteer enters the protocol.

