The risk of developing anemia due to blood draws during the study is uncommon but still possible in subjects with a pre-study hemoglobin at the lower limit of study eligibility (<12.0 grams, or <13.0 grams for weight <70.8 kg). Subjects in this circumstance will be advised to take iron during the study (ferrous sulphate 325 mg twice daily) as a precaution. Additional iron supplementation may be recommended as appropriate if a complete blood count (CBC) performed at the end of the study reveals a low hemoglobin.

The potential risks to the subjects associated with venipuncture needle sticks or IV catheter insertions include discomfort, possible bleeding/hematoma (~1/1000) at the site, rarely an infection, and uncommonly feeling faint from the procedure. These risks will be minimized by allowing only experienced nurses or doctors to insert intravenous lines. From

time to time, difficulty may be encountered in performing venipuncture or inserting an intravenous catheter even after several attempts. In this instance, a subject may be escorted by a physician or a research nurse from the CRC to the Imaging and Diagnostics Services Short Stay Unit located in Suite 2600 on the 2nd floor of UI Heath Hospital at [name] immediately across the skyway adjacent to the CRC, where a member of the IV-PICC Team will perform the venipuncture or insert the intravenous catheter using ultrasound guidance at no additional risk. The subject will subsequently be escorted back to the CRC to complete the particular study visit. Use of the IV-PICC Team may extend the CRC study visit by up to 2 hours.

The studies will be performed on the CCTS CRC, which provides staff that assists the P.I. Furthermore, the P.I. has staff trained and dedicated to performing these studies. All catheters will be inserted with meticulous use of sterile technique to avoid infection and great care will be taken to minimize any discomfort or complications associated with insertion. The catheters will be kept patent with heparinized saline to prevent clotting.

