- **Salsalate Treatment** – Salsalate use can cause the following adverse effects characteristic of salicylates in descending order of frequency: tinnitus, nausea, hearing impairment, rash and vertigo. These effects are transient, and resolve upon cessation of salsalate. Although cause and effect has not been established, the following less common adverse effects have also been reported: abdominal pain, abnormal hepatic function, anaphylactic shock, angioedema, bronchospasm, decreased creatinine clearance, diarrhea, gastrointestinal irritation, inflammation, bleeding or perforation, hepatitis, hypotension, nephritis, urticaria, myocardial infarction or cerebral vascular accident.

Tinnitus is an expected side effect of salsalate treatment that occurs more frequently at doses higher than the one proposed for this study. To minimize this side effect, subjects will be advised to begin by taking one capsule (i.e. 500 mg of salsalate in subjects receiving salsalate) the first day and increase the dose in one capsule increments every 3 days thereafter until the desired dose is achieved. If tinnitus occurs at any point in the upward dose titration or later on during the treatment, an affected subject will be advised to reduce the daily study medication dose in stepped one capsule increments every 3 days. In a previous study, this approach effectively resolved symptoms enabling subjects to complete the study while still maintaining therapeutic salicylate levels. The nature of any suspicious symptoms reported by a subject will be reviewed to determine whether there is actual tinnitus before the salsalate dose is reduced in the manner described. Vital signs and potential side effects will be monitored every 4 weeks during treatment when subjects report to the CRC to have their blood draw for a salicylate level. Liver function tests, BUN and creatinine levels will be drawn within 4 weeks after study completion to be certain that no lasting untoward hepatic or renal impairment has occurred.

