| Infection | Patient observation and vital signs | CRC R.N. | During the procedure | Blood draws performed under sterile technique; Instruct patient regarding infection signs and symptoms and importance of reporting these to the M.D.; Provide M.D. and CRC telephone number in the event of a problem. |
| Bleeding, bruising or anemia | Patient observation and communication | CRC R.N. | During procedure | Careful closure of stopcocks between blood draws; Meet hemoglobin IRB requirements. |
| Thrombosis | Observe blood flow during draws | CRC R.N. | Every blood draw to check patency of lines. | 0.9% NS infusion @ 30cc/hr throughout the test. |
| Hypoglycemia during FS-IVGTT infusion of insulin. | Patient observation and frequent glucose measurements | CRC R.N. and Research Nurse Study Coordinator | Every 1-10 minutes during the initial 1½ hours of the FS-IVGTT starting 20 minutes before the test, then every 20-30 minutes for the next 1½ hours. | Cessation of the infusions and intravenous glucose administration if patient becomes symptomatic (i.e. headache, shakiness, visual changes and palpitations) or glucose level falls below 70 mg/dl. |

- A participant will be monitored continuously during an entire CRC visit to undergo study procedures, and the PI will be present within the hospital and available by telephone, pager or e-mail throughout each visit. In the situation of an anticipated or an unanticipated Adverse Event (AE), a standard IRB Adverse Event Report Form will be sent to the CRC and IRB in a timely manner. This report will include a full description of the event, including the relationship of the AE as not related, possibly related, or definitely related to the study procedure. The PI, in consultation with the DSMB, will grade adverse events severity as follows (as recommended by the National Cancer Institute):

- 0 – “No adverse event or within normal limits or not clinically significant”
- 1 – “Mild AE, did not require treatment”
- 2 – “Moderate AE, resolved with treatment”
- 3 – “Severe AE, resulted in inability to carry on normal activities and required

- professional medical attention”
- 4 – “Life threatening or disabling AE”
- 5 – “Fatal AE”

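### The plan's hemoglobin limits are applied only to pre-entry values, and no blood count is visible before the second 666 ml block at about week 12

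*Combined protocol and SAP*

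**What the plan says.** Section 7.0 (Venipuncture / Venous Catheter Blood Sampling) uses the pre-study blood count to decide who needs individual review. The limit is 11.6 g, or 12.6 g for a woman under 70.8 kg. For that lighter group, "blood sampling will be limited to 10.5 ml/kg within an 8 week period". If low hemoglobin is due to iron deficiency, the count is repeated on iron until it is acceptable, but only up to the point of entry.

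The same section gives the volumes: 64 ml per HCG-ST, then "330 mL (66 tsp) during each CCT, and 272 mL (54 tsp) during each FS-IVGTT". Section 6.1 fixes the FS-IVGTT volume per sample: "A total of 272 ml of blood (8 ml/sample) will be collected during the entire procedure". Section 6.0 places all three tests in the first week and again in the last week, after 11 to 13 weeks of treatment.

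Section 7.0 accepts that the draws can cause anemia in women near the limits. It advises iron during the study below 12.0 g (below 13.0 g under 70.8 kg), and more iron "if a complete blood count (CBC) performed at the end of the study reveals a low hemoglobin". Table 1 in section 6.0 lists "Post-Study Safety Tests: CBC & CMP". For the visits in between, section 6.2 says: "We will also draw an additional 20 mL (4 tsp) to measure salicylate levels (Visits 1, 6, 7 and 8) and fasting lipid profiles". The section 11.0 risk table answers bleeding, bruising and anemia with "Careful closure of stopcocks between blood draws; Meet hemoglobin IRB requirements".

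**The concern.** The two test blocks take the same amount of blood, but the hemoglobin limits are checked before only one of them. After entry a woman has given at least 666 ml and has taken study drug for about 12 weeks. Section 7.0 lists "gastrointestinal irritation, inflammation, bleeding or perforation" among less common reported effects of salsalate, while stating that cause and effect is not established. If her hemoglobin has drifted below the level that would have prompted review or a cap at entry, the second block goes ahead on an out-of-date value. The risk-table instruction to meet the hemoglobin requirements cannot be verified at that point without a new measurement. Section 6.1 does repeat the pregnancy test before post-treatment testing, so the plan rechecks one safety condition there but not this one.

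Two smaller matters bear on the same safeguard. The screening OGTT volume is stated in two ways that disagree. The cap is also lower than the standard block for much of the weight range it covers, and the visible text does not say which draws are then reduced.

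**Working it through.** **1. The plan's own volumes.** Inputs are from sections 6.1, 6.2 and 7.0.

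- HCG-ST: 4 × 16 = 64 ml
- CCT: 90 + 3 × 80 = 330 ml
- FS-IVGTT: 34 × 8 = 272 ml
- One block: 64 + 330 + 272 = 666 ml
- First block with screening as stated (at most 22 ml, plus a 24 ml OGTT): 666 + 22 + 24 = 712 ml
- Screening plus both blocks: 2 × 666 + 46 = 1,378 ml

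Section 7.0 states ceilings of 750 ml per block and 1,500 ml in total. Both are reproduced.

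**2. When hemoglobin is known.** Reading the visible schedule in order:

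- Screening: CBC, repeated before entry if the volunteer is iron deficient.
- Visits 1 to 5: first block, 666 ml.
- Visits 6 and 7 (weeks 4 and 8): salicylate, vital signs and side effects. No CBC is named.
- Visits 8 to 12: second block, 666 ml.
- Post-study: CBC.

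Table 1 is damaged in the copy available, but its row label and the section 7.0 text agree that the later CBC comes at the end.

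**3. Distance to the limit.** A woman under 70.8 kg who enters at 12.6 to 12.9 g is neither reviewed nor capped, though she is advised to take iron. A net fall of 0.1 to 0.4 g would bring her to 12.5 g, inside the range that triggers both. This is a distance to a threshold. The documents give no expected fall.

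**4. Cap against block.** The cap equals one block at 666 / 10.5 = 63.4 kg. At the 70.8 kg limit it is 10.5 × 70.8 = 743.4 ml. If the 64 ml HCG-ST is kept in full, the CCT and FS-IVGTT (330 + 272 = 602 ml) absorb the shortfall:

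| Weight | Cap (ml) | Short of 666 ml | As share of 602 ml |
|---|---|---|---|
| 60 kg | 630 | 36 | 6% |
| 55 kg | 577.5 | 88.5 | 15% |
| 50 kg | 525 | 141 | 23% |

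Salicylate and lipid samples in the same window would add a few ml to each shortfall.

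**5. OGTT volume.** Sections 6.2 and 7.0 state 24 ml. Section 6.1 describes a 9 ml baseline sample and five more of 9 ml: 6 × 9 = 54 ml. First-block blood with maximum screening draws is then 666 + 22 + 54 = 742 ml rather than 712 ml, before salicylate and lipid samples. This leaves 750 − 742 = 8 ml under the stated ceiling. Screening plus both blocks becomes 2 × 666 + 76 = 1,408 ml. The 22 ml is a maximum, needed only when hormones were not measured earlier, so 742 ml is an upper figure.

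**The case against.** Several protections are in place. Anemia is given as an example under the exclusion criteria (section 4.2). Iron-deficient volunteers must reach an acceptable hemoglobin before entry, and iron is advised near the limits. Peptic ulcer, coagulopathy and anticoagulant use are excluded. Side effects are checked every four weeks, and the blocks are about 12 weeks apart, which the plan presents as longer than the usual interval between blood donations. All of this stands and lowers the risk. None of it measures hemoglobin before the second block.

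On the cap, the objection largely succeeds. A cap that falls below the default volume is doing what a cap is for. It is expressed per 8 weeks, so for women capped at entry it already covers the second block. The Study Visit Blood Sampling Plan, an appendix that is not visible, may set out the reduced draws and settle the OGTT volume. With anemia excluded and individual review in place, the number of capped women may be zero. A reader might infer from the 63.4 kg figure that the protocol contradicts itself, or that most women will breach the cap. The documents do not support either. The figure describes body weight among women who also have hemoglobin below 12.6 g and are still admitted, and no count of them is given.

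A further objection concerns the remedy. Repeating the entry review unchanged before Visit 8 could remove a treated woman just before her post-treatment primary measurement. That stands, and it shapes the fix.

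**Conclusion.** The point holds as a modest participant-safety gap: on the visible text, 666 ml is drawn at about week 12 with no hemoglobin value since entry. It concerns any woman who reaches the second block, and matters most for those who entered close to the limits. How many would have fallen below them cannot be estimated from the documents.

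Three stronger readings should be resisted. First, nothing here threatens the primary comparisons. Second, the salsalate section does not support saying that the drug will lower hemoglobin; it lists gastrointestinal bleeding as less common and of unestablished cause. Third, it might be inferred that the corrected OGTT volume breaks the plan's limits. It does not: 742 ml is below both the 750 ml ceiling and the 743.4 ml cap at 70.8 kg. Going over requires adding a share of the 20 ml for salicylate and lipids, and the text does not say how that 20 ml is split across visits.

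The OGTT discrepancy (24 against 54 ml) is a plain inconsistency. The missing reduction rule for capped women calls only for a cross-reference. The conclusion assumes that the unseen appendix does not already schedule a CBC before Visit 8.

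**What to change.** 1. Add a CBC to the blood already drawn at Visit 7 (week 8), about four weeks before the second block. If the value is below the section 7.0 limits, start or continue iron and have the case reviewed for safety. For women under 70.8 kg, apply the 10.5 ml/kg per 8 weeks cap to the second block. State that the participant is not withdrawn by default, and that the 64 ml HCG-ST, which carries the Aim 1 primary outcome, is kept wherever it is safe.
2. Correct the screening OGTT volume so that sections 6.1, 6.2 and 7.0 agree, and update the block total to match.
3. In section 7.0, cross-refer to the part of the Study Visit Blood Sampling Plan that says how sampling is reduced for a capped woman, or add a sentence if it does not. If the appendix already contains a CBC before Visit 8, cite it and item 1 falls away.

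The cost is 90 to 113 extra CBCs of a few ml each, at an existing visit. A CBC does not report a salicylate level, so the salicylate blinding arrangement is unaffected. A few women may have a reduced second CCT or FS-IVGTT draw, which would cost some Aim 2 or insulin-sensitivity data.
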